### **7.1.3 Adverse Events**

All AEs from the time a patient starts receiving study treatment through the period of patient follow-up (30 days after the last dose of study drug or until the start of new anti-cancer therapy, whichever is earlier) will be summarized (incidence) by the system organ class, preferred term, toxicity/severity grade, and causal relationship to TAS-114/S-1 or S-1 control.

The following adverse events summaries will be reported:

- Overall summary of safety including AEs, fatal AEs, treatment-related AEs, serious AEs, treatment-related serious AEs, AEs of grade 3 and above, AE leading to study drug interruption, AEs leading to study drug dose reduction, AEs leading to study drug administration
- Incidence rates of AEs
- Incidence rates of AEs related to study drug
- Incidence rates of serious AEs
- Incidence rates of serious treatment-related AEs
- Incidence rates of AEs by NCI-CTCAE v4.03 grade
- Incidence rates of AEs leading to study drug interruption by NCI-CTCAE v4.03 grade
- Incidence rates of AEs leading to study drug dose reduction by NCI-CTCAE v4.03 grade
- Incidence rates of AEs leading to study drug discontinuation by NCI-CTCAE v4.03 grade
- Incidence rates of non-serious AEs
- Incidence rates of AEs of special interest (based on the grouped AE terms in [Appendix 4](#))

Adverse events will also be summarized by geographical region.

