8.1.1. Study Duration

Patients will receive the study drug according to the proposed treatment schedule until progressive disease (PD), occurrence of intolerable side effects, removal by the Investigator, or withdrawal of consent. A patient is considered discontinued from study treatment when either TAS-114/S-1 or S-1 alone is discontinued.

For the purpose of the final analyses, the study will be considered completed when all patients have discontinued from treatment or a minimum of 12 months from the date of the first day of treatment with TAS-114/S-1 or S-1 of the last patient enrolled or until the target number of

events (deaths, n=80) is reached, whichever occurs last. This analysis may still be done even if there are patients still on treatment.

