14.2. Determination of Sample Size

The study is designed to differentiate 4.2 months median PFS of treatment with TAS-114/S-1 from 2.2 months median PFS of treatment with S-1 (hazard ratio of 0.524) with 80% statistical power and a 1-sided type 1 error of 0.05. Using a treatment allocation of 1:1 (TAS-114/S-1: S-1), a target of 60 events (PD or deaths) will be required for the primary analysis, which corresponds to 71 events based on investigator review under the assumption that the discrepancy in PD events between the independent central review and investigator review is 15%. A total sample size of 124 patients is planned from the assumption that accrual period is 10 months, the percentage of PFS events is 65%, and the percentage of patients lost to tumor follow-up caused by study discontinuation is 10%.

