### 3.5 Sample Size

The planned sample size is approximately 124 advanced or metastatic NSCLC patients. The study is designed to differentiate 4.2 months median PFS of treatment with TAS-114/S-1 from 2.2 months median PFS of treatment with S-1 (hazard ratio of 0.524) with 80% statistical power and a 1-sided type 1 error of 0.05. Using a treatment allocation of 1:1 (TAS-114/S-1: S-1), a target of 60 events (PD or deaths) will be required for the primary analysis, which corresponds to 71 events based on investigator review under the assumption that the discrepancy in PD events between the independent central review and investigator review is 15%. A total sample size of 124 patients is planned from the assumption that accrual period is 10 months, the percentage of PFS events is 65%, and the percentage of patients lost to tumor follow-up caused by study discontinuation is 10%.

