### 6.3.2 Extent of Exposure to Study Medication

The total dose received, number of treatment cycles received, and dose intensity will be derived using data from the TAS-114 and S-1 Administration form, and Study Drug Accountability form.

The **total dose received** for each study drug is the sum of dose received at each cycle, and the number of cycle received is the number of cycles with at least one dose taken during a cycle.

The **treatment duration** for each study drug (in weeks) is calculated from the date of first dose to the date of last dose + 7 or the start of new anti-cancer treatment, whichever is earlier, and then divided by 7.

**Dose intensity** is defined as the total dose actually received divided by the planned dose (i.e., total dose that would be given if no doses were missed and/or no dose reductions were made for the duration of time the patient received any component of study treatment) multiplied by 100%.

The planned dose for each drug at each cycle is as follows:

- TAS-114: 400 mg x 2 (BID) x 14 Days
- S-1: 30 mg/m^2 x BSA x 2 (BID) x 14 Days  
where BSA (m^2) = ([Body Weight (kg)]0.425 x [Height (cm)]0.725) x 0.007184.

The total planned dose is the sum of planned doses over all cycles.

The number of dose reductions, dose modifications, dose interruptions, and cycle delays will also be calculated.

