#### Adverse Events Counting Rules

1. A patient with more than one different adverse event in a particular system organ class (SOC) will be counted only once in the total of patients experiencing adverse events in that particular SOC.

2. A patient having experienced the same event (AE preferred term) more than once during the study will be counted only once in the number of patients with that event.
3. If an event changes in intensity or in seriousness during the study, it will be counted only once with the worst grade and seriousness respectively.
4. If the causal relationship to the study drug is assessed differently, it will be counted only once by considering the “Worst” documented degree of relationship.

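### The AE tables give only patient percentages over a window that depends on time to progression, with no common-window or time-at-risk summary beside them

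*SAP*

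**What the plan says.** - **AE summaries.** SAP 7.1.3 says that AEs from first dose to 30 days after last dose, or to new anticancer therapy if that is earlier, "will be summarized (incidence) by the system organ class, preferred term, toxicity/severity grade, and causal relationship to TAS-114/S-1 or S-1 control". Several listed tables are labelled incidence rates, but no person-time denominator is defined. Under the counting rules in SAP 6.3.3, a patient with a repeated event "will be counted only once in the number of patients with that event". The tables are therefore percentages of patients.
- **Treatment length.** Protocol 8.1.1 says: "Patients will receive the study drug according to the proposed treatment schedule until progressive disease (PD"; the other stopping reasons there are intolerable side effects, removal by the investigator and withdrawal of consent.
- **Design assumption.** Protocol 14.2 says the study is "designed to differentiate 4.2 months median PFS of treatment with TAS-114/S-1 from 2.2 months median PFS of treatment with S-1". Neither document states an assumption about time on treatment.
- **Exposure.** SAP 6.3.2 derives a treatment duration that "for each study drug (in weeks) is calculated from the date of first dose to the date of last dose + 7", or to new anticancer treatment if earlier. SAP 7.1.1 summarises total dose, cycles and dose intensity, and tabulates discontinuations with reasons by arm. Nothing links these to AE incidence.
- **Laboratory values.** SAP 7.1.5 plans Kaplan-Meier summaries by arm for time to worst grade 3 or 4 value and time to resolution. The visible text plans nothing comparable for AEs.

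**The concern.** Safety and tolerability is a stated secondary objective (Protocol 7.2), and S-1 is the only randomised comparator. The rationale for the combination is more antitumour activity with an acceptable change in toxicity, which is a comparative question.

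A patient percentage over an open-ended window mixes two things: how often events arise, and how long patients are watched. If the combination delays progression, its patients are watched longer, and an AE that keeps arising at the same rate in both arms will show a higher percentage in the combination arm. If combination patients stop early for toxicity, the distortion weakens or reverses. A reader of the planned tables could not tell these cases apart, and would have to judge the correction by eye from a separate exposure table.

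**Working it through.** **1. The plan's own figures.** From SAP 3.5, the design has medians of 4.2 and 2.2 months, "with 80% statistical power and a 1-sided type 1 error of 0.05", and 1:1 allocation. Schoenfeld events = 4 × (1.645 + 0.842)² / (ln 0.524)² = 59.1, so 60 as stated. Then 60/0.85 = 70.6, so 71; 71/0.65 = 109.2; 109.2/0.90 = 121.4. The planned 124 (62 per arm) is within 3 patients of that. The medians below are therefore the ones that drive the design.

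**2. Assumptions.** Time on treatment T is exponential with the design PFS medians. The AE hazard h is constant and identical in both arms. The documents give no AE hazard, so h is varied. The 30-day tail is 30/30.4375 = 0.986 month. Truncation by new therapy or death is ignored.

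**3. Length of the AE window, no data cut.**
- Stopping rates are ln 2/2.2 = 0.315 and ln 2/4.2 = 0.165 per month.
- Mean time on treatment is 3.17 and 6.06 months (ratio 1.91).
- The mean AE window is 3.17 + 0.986 = 4.16 and 6.06 + 0.986 = 7.04 months (ratio 1.69).

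**4. With a data cut C.** Accrual is taken as uniform over the planned 10 months, and the mean of min(T + 0.986, C) is simulated.
- Cut 12 months after accrual ends: 4.13 and 6.57 months, ratio 1.59.
- Cut 3 months after accrual ends, the earliest primary analysis under Protocol 14.1.2.1 provided 60 events have been reached: 3.65 and 4.92 months, ratio 1.35.

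**5. Crude incidence with no true difference.** With no cut, P = 1 − e^(−0.986h) × λ/(λ + h), where λ is the stopping rate. At h = 0.10:
- S-1: 1 − 0.906 × 0.315/0.415 = 31.2%
- Combination: 1 − 0.906 × 0.165/0.265 = 43.6%

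With a cut, P = 1 − mean of exp(−h × min(T + 0.986, C)). S-1 versus combination, gap in points in brackets:

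| h per month | No cut | Cut at 12 months | Cut at 3 months |
|---|---|---|---|
| 0.05 | 17.8% v 26.9% (9.1) | 17.8% v 26.1% (8.3) | 16.2% v 21.0% (4.9) |
| 0.10 | 31.2% v 43.6% (12.4) | 31.2% v 42.9% (11.8) | 29.0% v 36.5% (7.6) |
| 0.15 | 41.6% v 54.8% (13.2) | 41.5% v 54.4% (12.9) | 39.3% v 48.2% (8.9) |
| 0.30 | 61.9% v 73.6% (11.7) | 61.9% v 73.5% (11.6) | 60.2% v 69.6% (9.4) |

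Outside this range the gap is smaller: with no cut, 4.7 points at h = 0.02 and 3.7 at h = 1.0.

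**6. What removes the gap** (h = 0.10, no cut).
- An extra toxicity-stopping rate of 0.06 per month in the combination arm gives 31.2% v 37.3%. At 0.15 per month the arms are equal at 31.2%.
- If AEs arise only in the first one or two cycles, the ratio of percentages is 1.00 to 1.01.

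**7. Do the alternatives behave?**
- Constant hazard: the simulated first-event rate at h = 0.10 is 0.0998 v 0.1001 per patient-month, ratio 1.00, against a crude ratio of 1.40.
- Front-loaded hazard, identical in both arms (0.30 per month for 6 weeks, then 0.03): crude ratio 1.12, first-event rate ratio 0.73, first-6-weeks incidence ratio 1.01. The rate alone would show a spurious advantage for the combination.
- Six weeks is 42/30.4375 = 1.38 months. The share of patients whose AE window covers it is exp(−λ × (1.38 − 0.986)), or 88% for S-1 and 94% for the combination, so observation is nearly balanced.

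**The case against.** - **Time on treatment is not PFS.** Primary PFS uses central review, whereas treatment decisions follow the investigator (Protocol 12.1). Treatment also stops for clinical progression, a dose delay over 14 days, or need for more than two reductions (Protocol 8.3.1). In the combination arm, permanently stopping either drug counts as discontinuation (Protocol 8.3). This stands: the exposure gap is an inference and may be smaller or absent.
- **Safety is descriptive.** The protocol synopsis says so, and no between-arm AE test is planned. The percentage of patients affected under treatment as given is a legitimate quantity. This also stands, and is why the crude tables should stay. They do not, however, answer the comparative question alone.
- **Some handling exists.** Exposure is reported by arm, and grade 3 or 4 laboratory values have censoring-aware summaries. True, but neither is tied to the AE tables.
- **Sampling error is larger.** With 62 per arm, the 95% half-width for 31.2% v 43.6% is 1.96 × √[(0.312 × 0.688 + 0.436 × 0.564)/62] = 16.9 points. One row proves little. But the artefact pushes every sustained AE row the same way, so a reader may see a pattern.
- **Incomplete view.** Parts of the SAP are redacted and its appendices are not shown, so this point rests on the visible text.

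A reader might go further and infer that the trial is designed for twice as long on treatment, that the AE window doubles, or that the tables must show excess toxicity for the combination. The documents do not support this. The 1.91 ratio belongs to PFS medians; the SAP's window includes the 30-day tail, which brings the ratio to 1.69 before any data cut; and the direction depends on who stops and why.

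**Conclusion.** The point holds as a cheap improvement to the SAP, not as an error in it. The planned AE tables cannot separate a difference in toxicity from a difference in observation time. If the design PFS medians carry over to time on treatment, the mean AE window is about 1.35 to 1.7 times longer in the combination arm, and equal sustained hazards of 0.05 to 0.30 per month would appear as an excess of about 5 to 13 points.

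That size rests on exponential time on treatment, a constant AE hazard, and hazards that are assumed. Larger excesses, up to 16 points, appear only if the 30-day tail is left out, which is not the SAP's window.

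It would also be wrong to conclude that safety should rest on rates per patient-month: the front-loaded case shows that such a rate can err in the opposite direction.

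**What to change.** In SAP 7.1.3, keep the crude percentages and label them descriptive. For the overall, Grade 3 or higher, serious, treatment-related and special-interest AE summaries, add:

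1. Incidence over a common window of the first 6 weeks (Cycles 1 and 2), by arm, with the difference and 95% CI.
2. As a supporting summary, the first-event rate per patient-month at risk, with time at risk ending at first event, 30 days after last dose or new anticancer therapy, whichever is earliest. Show treatment duration by arm beside it; SAP 6.3.2 derives this, but SAP 7.1.1 does not list it.

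State that the rate assumes a roughly constant hazard and can mislead for early-onset toxicity, that the two summaries are read together, and that neither alone is the basis for the safety conclusion.

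In the same edit, reconcile SAP 6.3.3, whose treatment-emergent definition runs to 30 days after last dose without a stop at new therapy, with SAP 7.1.3, which has that stop. The choice defines time at risk.

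The cost is SAP wording and a few table columns from dates already collected. The 6-week window does not capture late toxicity, which is why the rate and the crude table stay beside it.

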### **7.1.4 Deaths**

Summaries of number of deaths and cause of death will be produced by treatment group.

### **7.1.5 Laboratory Data**

Hematology, serum chemistry, and coagulation results will be summarized by toxicity grade (using NCI-CTCAE v4.03 toxicity grading – see [Appendix 1](#) at baseline and post-baseline measurements that worsened by at least one grade. Local laboratory ranges will be used for grading. In the event a range is not available a standard set of lab ranges as detailed in [Appendix 3](#) will be utilized and flagged in the database.

The worst change from baseline in toxicity grade for selected laboratory parameters will also be presented in shift tables: in each treatment arm, the patient's baseline grade will be cross-tabulated by the patient's maximum post-baseline grade during the treatment.

Time to maximum/worst grade 3 or 4 value and time to resolution will be summarized for all quantitative laboratory parameters if toxicity grade is defined in NCI-CTCAE v4.03. The Hematology parameters will include Hemoglobin, Hematocrit, RBC, WBC, ANC, Thrombocytopenia, and Platelets, and the Chemistry

parameters will include AST, ALT, Total Bilirubin, and Alkaline Phosphatase. Count of the events and the censored, minimum and maximum of the event time will be presented by treatment group. Meanwhile, median time to worst grade 3 or 4 value and time to resolution for each group being compared will be estimated using the Kaplan-Meier method, along with the corresponding 95% CI.

The qualitative urinalysis results will be summarized by visit and treatment groups. A shift table for qualitative urinalysis results from baseline to worst past-baseline will also be presented.

#### **7.1.6 Vital Signs**

Vitals signs (systolic/diastolic blood pressure, heart rate, respiratory rate, temperature, and weight) and their changes from baseline will be summarized by visit.

#### **7.1.7 Concomitant Medications and Therapies**

Concomitant medications will be summarized by treatment groups and sorted alphabetically by Anatomical-Therapeutic-Chemical classification (ATC) class and preferred drug name.

#### **7.1.8 Other Diagnostics and Procedures**

Other diagnostics and procedures will be summarized by treatment groups.

#### **7.1.9 New Anti-Cancer Treatments**

New anti-cancer treatments will be summarized by treatment groups. The number and percentage of patients receiving any chemotherapy, radiotherapy, surgery, immunotherapy, and other treatments will be summarized descriptively for the ITT population. The number of regimens received by each patient will also be summarized.

#### **7.1.10 Other Safety Assessments**

Results from the electrocardiogram and the ECOG performance status will be summarized by visit.

CCI

**Statistical Analysis Plan**

Protocol No. TO-TAS-114-201

Last Revision Date: 29NOV2017

CCI

CCI

## **8. CHANGES FROM METHODS PLANNED IN THE PROTOCOL**

Time to treatment failure is added as a post hoc analysis.

Any changes to methods planned in this statistical analysis plan will be documented in a revision to this statistical plan prior to database lock, or identified in the clinical study report.

## **9. STATISTICAL SOFTWARE**

SAS Version 9.4 in the UNIX environment will be used for all statistical analyses.

